Study Number	AFT-25
Study Type/Phase	Interventional Phase III Randomized Clinical Trial
Clinical Indication	Low-risk ductal carcinoma in situ (DCIS)
ClinicalTrials.gov Identifier	NCT02926911
IND Number	Not applicable
Number of Trial Patients	1,080
Estimated Duration of Trial	Accrual: 78 months (07/01/16- 12/31/22) Follow up: 2-, 5-, 7- and 10-years
Rationale	To study the risks and benefits of active monitoring (AM) compared to surgery in the setting of a pragmatic prospective randomized trial for low-risk DCIS. Our overarching hypothesis is that management of low-risk DCIS using an AM approach does not yield inferior invasive breast cancer or quality of life outcomes compared to surgery.

Primary Objective	To assess whether 2-year ipsilateral invasive breast cancer rate for AM is non-inferior to that for surgery.
Secondary Objectives	To determine whether AM is non-inferior to surgery for the following outcomes: 2-, 5-, 7- and 10-year mastectomy rate, breast conservation rate, contralateral invasive breast cancer rate, overall survival and invasive breast cancer specific survival; health-related QOL, anxiety and depression at baseline, 6 months, 1 year, annually year 2-6, biannually thereafter; coping at baseline; intolerance of uncertainty at baseline and 2 years.
Trial Design and Schema	Multicenter Phase III Prospective Randomized Trial comparing surgery to active monitoring with option of endocrine therapy (in both arms) for low-risk ductal carcinoma in situ (DCIS) (see Study Schema below)

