2.2 Secondary Objectives

2.2.1 Quality of life and psychosocial outcomes:

The secondary hypothesis is based upon a non-inferiority endpoint that **2-, 5-, 6, 8, 10 health-related quality of life, rate of anxiety, and rate of depression are not inferior in the AM group compared to the surgery group.**

2.2.2 Clinical outcomes:

The secondary hypothesis is based upon a non-inferiority endpoint that **2-, 5-, 7- and 10-year rates of mastectomy, contralateral invasive breast cancer, and survival (both overall survival and invasive breast cancer-specific survival) are not inferior in the AM group compared to the surgery group.**

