2.3 Endpoints

2.3.1 Primary endpoint:

Proportion of new diagnoses of ipsilateral invasive breast cancer in surgery and AM arms at follow up of 2-years.

2.3.2 Secondary endpoints:

- Quality of life and psychosocial outcomes;
 - Health related QOL at baseline, 6 months, 1 year, annually year 2-6, biannually thereafter.
 - Anxiety/depression at baseline, 6 months, 1 year, annually year 2-6, biannually thereafter.
 - Coping at baseline
 - Intolerance of uncertainty at baseline and 2 years
- Clinical outcomes
 - Mastectomy rate at 2, 5, 7 and 10 years
 - Breast conservation rate at 2, 5, 7 and 10 years
 - Contralateral invasive breast cancer rate at 2, 5, 7 and 10 years
 - Overall survival and invasive breast cancer-specific survival at 2, 5, 7, and 10 years
 - Ipsilateral invasive breast cancer rate in surgery and AM arms at 5, 7 and 10 years

2.3.3 Exploratory endpoints:

- Breast MRI utilization at 2, 5, 7 and 10 years
- Breast biopsy rate at 2, 5, 7 and 10 years
- Radiation rate at 2, 5, 7 and 10 years
- Chemotherapy rate at 2, 5, 7 and 10 years
- Self-reported co-morbidity at baseline, 6 months, 1 year, annually year 2-6, biannually thereafter.
- Adherence to hormonal therapy at 6 months, 1 year, annually year 2-6, biannually thereafter.
- Health behavior/lifestyle factors at 6 months and 2 years
- Symptoms, pain, body image, sexual function at baseline, 6 months, 1 year, annually year 2-6, biannually thereafter.

- Quality of decision making at baseline and 2 years
- Decisional regret at 1 year, annually year 2-6, biannually thereafter.
- Knowledge and risk perceptions at baseline and 2 years
- Decisional conflict at baseline
- Financial burden at 6 months
- Employment status at baseline, 6 months, 1 year, annually year 2-6, biannually thereafter.
- Use of complementary therapies at 6 and 24 months

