10.2 Sample Size, Accrual Time and Study Duration

Power and Sample Size Considerations. Sample size for this study was estimated using a 2-group test of non-inferiority of proportions, with the 2-year invasive breast cancer rate in the surgery group assumed to be 0.10 based on published studies.^{61,62} The non-inferiority margin assumed was 0.05. Based on a 1-sided un-pooled z-test, with alpha=0.05, a sample size of n=446 per group will have 80% power⁶⁴ to detect the specified non-inferiority margin. The proportion of patients who decline the arm to which they are specifically randomized can diminish the estimate of treatment difference, and could also widen the confidence bounds, but the analytical approaches proposed here aim to diminish the impact on bias of the treatment difference. With a 3-year duration of accrual and 2 additional years of follow-up, we anticipate approximately 148 total events.

Analysis of Primary Outcome (See below for outcomes definitions). This trial was designed anticipating non-acceptance of arm allocation, and the proportion of patients that do not accept their arm allocation can lead to bias in estimates of treatment differences. Thus, we plan to complete several analyses of the primary outcome, reporting the primary intent to treat (ITT) analysis as well as sensitivity analyses that are intended to reduce the bias in estimation of treatment difference in this setting.

We assume that a clinically acceptable difference in 2-year invasive cancer diagnosis rate in order to conclude non-inferiority is 5%. Cumulative incidence curves will be used to estimate the invasive cancer diagnosis rates over time, and at the 2-year point, the difference in rates will be estimated and a 1-sided upper confidence bound of (AM-GCC) will be computed, using methods described by Austin.⁶⁵ We will conclude that AM is not inferior to Surgery if the upper confidence bound on the risk difference at 2 years is less than 5%.

ITT Analysis. The ITT analysis of 2-year invasive cancer diagnosis rate will be conducted using all patients, as randomized, and will be completed using Kaplan-Meier estimates, stratified by group, combined with the Greenwood's confidence interval. The difference in invasive cancer risks will be computed from the Cox model with treatment at 2 years, with a 1-sided 95% confidence interval of the difference (AM-GCC) computed.

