Planned subgroup analyses (NCDB Special Study). The large DCIS registry developed through collaboration with the National Cancer Database (NCDB) will allow for the continued collection of long-term outcomes for patients as well as for the comparison of primary and secondary outcomes (when measurable in NCDB) for **AM versus surgery** amongst those patients who are randomized and accept their arm allocation versus those patients who are randomized but do not accept their arm allocation versus patients not registered or randomized to COMET, but who generally meet our broad inclusion criteria for the trial. Patients will be identified from all study sites during the time interval of COMET accrual. These analyses will be from predominantly non-randomized patients, so we plan to utilize observational study approaches for analyses. We will use full regression models (logistic or Cox model, dependent upon outcome measure) to control for potential confounders, including pathology, age, race, academic versus community setting, among others. As in other analyses, we will utilize inverse-probability weighting to handle missing data.⁷⁰

Analyses of long-term outcomes. Analyses of long-term outcomes will follow the approaches outlined above, modifying the year of rate calculations, accordingly. PRO data will utilize longitudinal linear mixed models over time, following appropriate scoring and transformation, if needed.

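### Thirty-one secondary non-inferiority hypotheses are posed as conclusions to be drawn, with no gate on the primary, testing order, multiplicity control or descriptive label

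*Combined protocol and SAP*

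**What the plan says.** The synopsis introduces the secondary objectives as questions to be settled: "To determine whether AM is non-inferior to surgery for the following outcomes: 2-, 5-, 7- and 10-year mastectomy rate", followed by breast conservation, contralateral invasive cancer, the two survival outcomes and the patient-reported outcomes. Section 2.2.2 states a secondary non-inferiority hypothesis for "2-, 5-, 7- and 10-year rates of mastectomy, contralateral invasive breast cancer, and survival", with survival meaning both overall and invasive breast cancer-specific survival. Section 2.2.1 states one that "health-related quality of life, rate of anxiety, and rate of depression are not inferior in the AM group compared to the surgery group", at years 2, 5, 6, 8 and 10. Section 2.3.3 has a separate exploratory list, and these outcomes are not in it.

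A level and a margin are stated once, for the primary. Section 10.2 uses a one-sided alpha of 0.05 and a 5-point margin for 2-year invasive cancer, "with a 1-sided 95% confidence interval of the difference (AM-GCC) computed" (GCC is the former name of the surgery arm). For later time points, section 10.2 says: "Analyses of long-term outcomes will follow the approaches outlined above, modifying the year of rate calculations, accordingly". Its next sentence sends the patient-reported data to longitudinal linear mixed models. Section 10.5 adds t-tests, ANOVA and McNemar's test, again with no margin or bound.

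Section 11.14 says that the 2-year results will be published first and that analyses at 5, 7 and 10 years will follow.

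**The concern.** The secondary objectives are worded as conclusions about non-inferiority, and the sponsor has kept them apart from the exploratory tier. Yet the plan does not say which of them carries weight, in what order they are judged, or whether any may be claimed if the primary fails. A report that follows the plan could state that AM is non-inferior for mastectomy or survival at some year after a failed primary, and nothing in the plan would mark that statement as unprotected. In a trial of omitting surgery, such statements would be read as evidence.

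The gap is of a different kind for the patient-reported outcomes. They have hypotheses but no decision rule, so the criterion for non-inferiority could be set after the data are seen. No single quality-of-life score or visit is named, although the overarching hypothesis in section 1.4 includes quality of life.

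**Working it through.** **1. Primary calculation.** Inputs from section 10.2: "2-year invasive breast cancer rate in the surgery group assumed to be 0.10"; margin 0.05; "Based on a 1-sided un-pooled z-test, with alpha=0.05, a sample size of n=446 per group will have 80% power". With the AM rate also taken as 0.10,

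n per group = (z₀.₉₅ + z₀.₈₀)² × [0.10×0.90 + 0.10×0.90] / 0.05² = (2.4865)² × 0.18 / 0.0025 = 445.1, rounded up to 446.

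This matches the plan. The stated level is used in full by the one primary test. No sample size or error rate is given for any secondary hypothesis.

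**2. Count.**

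| Family | Source | Outcomes × years | Hypotheses |
|---|---|---|---|
| Clinical | 2.2.2 | 4 × 4 (2, 5, 7, 10) | 16 |
| Patient-reported | 2.2.1 | 3 × 5 (2, 5, 6, 8, 10) | 15 |
| Total | | | 31 |

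The synopsis adds breast conservation at four years (31 + 4 = 35). Section 2.2.2 does not list it.

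**3. Decision rule for each family.**
- Clinical: the long-term paragraph of 10.2 changes only the year. The only non-inferiority rule above it is the one-sided 95% bound. An unadjusted one-sided 5% test is therefore the natural reading, but it is an inference. No margin is stated for these outcomes.
- Patient-reported: no level, margin or non-inferiority test is stated. No error rate can be computed, so these 15 are left out of what follows.

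**4. Error rate for the 16 clinical hypotheses.** Assumptions: each is tested at one-sided 0.05; every true difference sits exactly at its margin, whatever that margin is; the test statistics share a common correlation ρ. The documents give no correlations, so a range is shown. Under independence the chance of at least one false claim is 1 − 0.95¹⁶ = 56.0%. Otherwise it is

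1 − ∫ Φ[(1.645 − √ρ·x)/√(1−ρ)]¹⁶ φ(x) dx.

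| ρ | Chance of at least one false claim |
|---|---|
| 0 | 56% |
| 0.2 | 45% |
| 0.5 | 31% |
| 0.8 | 18% |
| 0.9 | 13% |

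A simulation closer to the actual structure took correlation 0.5 between outcomes and correlation decaying over time. It gave about 26% with 0.9 between adjacent years and about 33% with 0.7, both inside the range above.

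**5. If only some outcomes sit at their margins.** For m such hypotheses, taken as independent, with the rest comfortably non-inferior, the rate is 1 − 0.95ᵐ: m = 1 gives 5.0%, m = 2 gives 9.8%, m = 3 gives 14.3%, m = 5 gives 22.6%.

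**6. Search for any control.** Sections 10.1 to 10.10 and 11.14 contain no gate, order, alpha split or key-secondary designation. The remark in 10.2 about maintaining the alpha level concerns the choice among approaches to patients not accepting their allocation. It does not concern multiplicity.

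**The case against.** The strongest reply is that the error rates describe an extreme case. A false claim needs an outcome that is truly at or beyond its margin, and not all of these are likely to be. AM patients have no primary surgery (section 5.2.2.1), while section 1.1.2 reports that 23.8% of women with DCIS had a mastectomy in 1991 to 2010, so early mastectomy rates should favour AM. Without stated secondary margins, the actual error rate is unknown. This stands, and it is why the figures are given as conditional and with the smaller cases beside them.

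Three stronger readings are tempting, and the documents do not support them.

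- *All 31 hypotheses are tested at a full one-sided 5%.* A reader might then quote 1 − 0.95³¹ = 80% under independence. Sections 10.2 and 10.5 give the patient-reported outcomes no such test, so that figure has no basis for 15 of the 31.
- *The family has 38 members.* This adds "Ipsilateral invasive breast cancer rate in surgery and AM arms at 5, 7 and 10 years" to the 35. Section 2.3.2 lists these as endpoints, but neither section 2.2 nor the synopsis poses them as non-inferiority hypotheses.
- *The patient-reported family is undefined.* Section 2.2.1 names five years. The longer list in the synopsis and section 2.3.2 reads as the assessment schedule: it includes baseline, where a comparison of the effect of the arms has no meaning. The synopsis does place that schedule under its non-inferiority wording, which is loose and should be tidied.

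It can also be said that fixed years and the reporting commitment in 11.14 prevent free choice of the time point. That is largely right for the clinical outcomes. It limits selective reporting, but it supplies neither a gate nor an order.

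**Conclusion.** The concern holds in this form: 31 secondary non-inferiority hypotheses are posed as conclusions, with no gate on the primary, no order, no multiplicity control and no descriptive label.

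For the 16 clinical hypotheses, the chance of at least one false claim is about 13% to 45% for correlations of 0.9 to 0.2, and 56% under independence. This rests on two conditions: that the primary's one-sided 95% bound carries over unadjusted, which the plan implies but does not state, and that all 16 sit at their margins. With one outcome at its margin there is no excess over 5%. For the 15 patient-reported hypotheses the defect is the missing decision rule, and no percentage should be attached to it.

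A reader might infer that every secondary claim carries a known, several-fold excess over 5%. The documents do not support that unconditional statement. Nor is the trial's main conclusion in doubt, since the primary test and the 446 per group are untouched. This is a change that should be made, not one on which the validity of the primary analysis depends.

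**What to change.** In sections 2.2 and 10.2:

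1. State that any secondary non-inferiority conclusion requires the primary ITT test to succeed first.
2. State that secondary outcomes and time points are reported as differences with confidence intervals and without a non-inferiority conclusion.
3. If the sponsor wants some confirmatory secondary claims, name a few. Give each one time point, a justified margin and a one-sided level, and test them in a fixed order, stopping at the first failure. The order should follow the calendar of the analyses, with 2-year outcomes before 5-year outcomes. Otherwise a 5-year result placed early would hold back every 2-year secondary conclusion, against the reporting order in section 11.14.
4. Align the patient-reported time points under the synopsis's non-inferiority objective with section 2.2.1, and keep the assessment schedule separate.

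Steps 1, 2 and 4 are wording only and leave the primary test and sample size unchanged. The cost is that most secondary outcomes lose confirmatory status. Step 3 costs more, because each retained margin has to be chosen and defended.

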2.3 Endpoints

2.3.1 Primary endpoint:

Proportion of new diagnoses of ipsilateral invasive breast cancer in surgery and AM arms at follow up of 2-years.

2.3.2 Secondary endpoints:

- Quality of life and psychosocial outcomes;
 - Health related QOL at baseline, 6 months, 1 year, annually year 2-6, biannually thereafter.
 - Anxiety/depression at baseline, 6 months, 1 year, annually year 2-6, biannually thereafter.
 - Coping at baseline
 - Intolerance of uncertainty at baseline and 2 years
- Clinical outcomes
 - Mastectomy rate at 2, 5, 7 and 10 years
 - Breast conservation rate at 2, 5, 7 and 10 years
 - Contralateral invasive breast cancer rate at 2, 5, 7 and 10 years
 - Overall survival and invasive breast cancer-specific survival at 2, 5, 7, and 10 years
 - Ipsilateral invasive breast cancer rate in surgery and AM arms at 5, 7 and 10 years

2.3.3 Exploratory endpoints:

- Breast MRI utilization at 2, 5, 7 and 10 years
- Breast biopsy rate at 2, 5, 7 and 10 years
- Radiation rate at 2, 5, 7 and 10 years
- Chemotherapy rate at 2, 5, 7 and 10 years
- Self-reported co-morbidity at baseline, 6 months, 1 year, annually year 2-6, biannually thereafter.
- Adherence to hormonal therapy at 6 months, 1 year, annually year 2-6, biannually thereafter.
- Health behavior/lifestyle factors at 6 months and 2 years
- Symptoms, pain, body image, sexual function at baseline, 6 months, 1 year, annually year 2-6, biannually thereafter.

- Quality of decision making at baseline and 2 years
- Decisional regret at 1 year, annually year 2-6, biannually thereafter.
- Knowledge and risk perceptions at baseline and 2 years
- Decisional conflict at baseline
- Financial burden at 6 months
- Employment status at baseline, 6 months, 1 year, annually year 2-6, biannually thereafter.
- Use of complementary therapies at 6 and 24 months

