1.4 Study Design Rationale

The overarching hypothesis of the study is that management of low-risk DCIS using an active monitoring (AM) approach does not yield inferior invasive breast cancer or quality of life outcomes compared to surgery. The two arms of the trial were initially referred to as “active surveillance” and “guideline-concordant care”. However, the study team decided that “active monitoring” was a more proactive and appropriate term than “active surveillance”, and that “surgery” better described the primary treatment that patients would receive - as opposed to “guideline-concordant care”, a term that many patients found difficult to understand.

The **primary comparator groups** are “**surgery**” and “**active monitoring (AM)**” groups for biopsy confirmed diagnosis of low-risk DCIS (see Eligibility Criteria) (date of diagnosis is defined as the date of the first pathology report that diagnosed the patient with DCIS). As a pragmatic study, patients randomized to the surgery group will choose any of the NCCN standard treatment options for DCIS¹⁵ (with or without endocrine therapy), as they have all been shown to yield comparable breast cancer-specific survival.^{16,42} Patients randomized to the AM group choose either AM without endocrine therapy, or AM with endocrine therapy, and adherence/duration of therapy noted. Randomization will be stratified based on the following factors: **age at diagnosis**: <55, 55-65, >65; **maximum diameter of microcalcifications**: <2cms, 2-5cms, >5cms; DCIS nuclear **grade**: I or II. We will collect whether the patient has had prior surgical excision for the index diagnosis; this variable will be used for subset analysis and not stratification.

Given the numerous variables for which stratification is not planned, selection biases may occur. Thus, key covariates will be collected and included in the analysis to help overcome and adjust for inherent treatment biases expected within study arms. All eligible patients must be willing to undergo either surgery or AM prior to randomization, and must not have contraindication for surgery.

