1.6 Risks and Benefits

Surgery is, by definition, the prevailing standard of care for DCIS. The risks associated with surgical management of a breast lesion are well documented and include, but are not limited to, surgical and anesthetic side effects and/or complications; side effects and complications of subsequent radiotherapy following breast conservation therapy, if utilized; side effects and complications of endocrine therapy, if prescribed and taken. All local treatments may also be associated with a negative impact on cosmesis.

For surgery, the potential benefits (while uncertain on an individual patient basis) include reduced incidence of invasive breast cancer and reduced recurrence of DCIS or invasive breast disease. For endocrine therapy the impact on ipsilateral DCIS or recurrence/invasive breast cancer is uncertain, although there is a clear population-based reduction in contralateral DCIS and invasive breast cancer.

For AM, the risk of progression of DCIS to more extensive involvement of the breast or to developing invasive breast cancer is a key clinical outcome of the trial. The greatest potential risk to patients is posed by the delay in diagnosis of invasive breast cancer as a result of understaging on core biopsy. Among women who are diagnosed with low or intermediate grade DCIS without invasive breast cancer on core biopsy, the estimate of upstaging to invasive cancer upon surgical excision ranges from 0-20% in published literature.⁶⁰⁻⁶² One recent study,⁶² reported a 0% upstaging among women who would have fulfilled criteria for the LORIS trial, indicating that a low risk subgroup could be identified. The impact of a delay in diagnosis of invasive breast cancer or the development of invasive breast cancer while undergoing monitoring is thought to pose a low risk to patients if detected at an early stage, although this has not been definitively shown.

Additional risks to study participation include potential distress and loss of privacy when answering questions when filling out the surveys. While the direct responses to the survey will not be shared with the participants' medical team directly, we will alert the study team (registering physician and study coordinator at site) if a participant scores 10 or greater indicative of substantial depressive symptoms on the CES-D-10.

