2.1 Primary Objectives

The hypothesis is based upon a non-inferiority endpoint that ***2-year rate of invasive breast cancer diagnosis is not inferior in the AM group compared to the surgery group.*** The estimate of invasive breast cancer upstaging (i.e. identified at the time of surgery) is 10% in the surgery group. Non-inferiority will be

declared if the 2-year detection of invasive breast cancer in the AM group does not exceed 15% (based on statistical estimates).

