6.1. Assessment Types

6.1.1 Clinical Examination Assessment Plan

For both the surgery and AM groups, required clinical follow-up **years 1-5** will consist of:

- Clinical examination including history and physical examination every 6 months.
- Unilateral mammography (MMG) of the affected breast every 12 months in the surgery arm; not required if patient has had mastectomy of the affected breast.
- Unilateral mammography (MMG) of the affected breast every 6 months in the AM arm.
- MMG of the unaffected breast every 12 months in both arms; not required if patient has had mastectomy of the unaffected breast.
- All mammograms should be performed within 4 weeks of each clinic visit.

For the surgery and AM groups, required clinical follow-up **years 6-10** consists of:

- Clinical examination including history and physical examination every 12 months (both arms).
- Bilateral mammogram every 12 months (both arms) (*mammogram not required if patient has had mastectomy of both the index and the unaffected breast*).
- For patients on the AM arm, the study does not require 6-monthly MMG after the 5-year timepoint. However, *the decision about whether to continue 6-monthly MMG should be at the discretion of the patient in consultation with their treating physician*.
- The study does not recommend the use of endocrine therapy after the 5-year timepoint. However, *the decision about whether to continue ET should be at the discretion of the patient in consultation with their treating physician*.

Standardized case report forms will be completed for each scheduled study visit. In the surgery group, treatment data, including surgery and radiation if received, will be collected. For both groups, the use of endocrine therapy will be recorded. We will also collect clinical outcomes, including procedures, interventions, and recurrence history since the last visit. More frequent clinic visits or additional imaging studies other than those required by the study protocol will be accommodated and recorded. All radiology

and pathology reports as well as the primary source image data will be uploaded to the ALLIANCE central imaging data submission portal.

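### At 2 years occult invasion is found by excision in one arm and by triggered biopsy in the other, which favours non-inferiority; no sensitivity analysis addresses this, and no endpoint directly records size, nodes or stage at invasive diagnosis

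*Combined protocol and SAP*

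**What the plan says.** Section 2.3.1 gives the primary endpoint as "Proportion of new diagnoses of ipsilateral invasive breast cancer in surgery and AM arms at follow up of 2-years". Section 10.2 sizes the trial "with the 2-year invasive breast cancer rate in the surgery group assumed to be 0.10 based on published studies", and adds: "The non-inferiority margin assumed was 0.05". Non-inferiority is declared if the one-sided upper bound on AM minus surgery at 2 years is below 5%.

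Section 2.1 says where the 10% comes from: "The estimate of invasive breast cancer upstaging (i.e. identified at the time of surgery) is 10% in the surgery group". Section 5.1.2.1 expects that surgery within 60 days of randomization. Section 5.2.2.1 gives AM women no primary surgery. Section 6.1.1 gives them an examination and a mammogram of the affected breast every 6 months in years 1-5, and section 6.1.2 leaves biopsy to clinical judgment, guided by listed criteria. No tissue assessment at 2 years is planned in AM.

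Section 1.6 says that the greatest potential risk is posed by "the delay in diagnosis of invasive breast cancer as a result of understaging on core biopsy", and that the presumed low impact of such a delay has not been definitively shown. On prevalence it says that "the estimate of upstaging to invasive cancer upon surgical excision ranges from 0-20% in published literature". The secondary endpoints in 2.3.2 include the ipsilateral invasive rate at 5, 7 and 10 years and invasive breast cancer-specific survival. Chemotherapy rate is exploratory (2.3.3). None records tumour size, nodal status or stage.

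**The concern.** The planned surgery-arm rate is mainly invasion already present at entry. Randomization gives AM the same occult pool, but the two arms look for it by different means and at different times. Each occult cancer that AM has not found by 2 years lowers the AM rate. In a one-sided non-inferiority comparison, that error runs toward the conclusion being sought.

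A favourable 2-year result therefore cannot by itself separate two explanations: AM does not lead to more invasive cancer, or some of it has not yet been found. Nor would the listed endpoints show directly whether cancers found later in AM are larger or more often node-positive. This matters because section 1.4 states the overarching hypothesis as AM that "does not yield inferior invasive breast cancer or quality of life outcomes compared to surgery", and section 11.14 plans the first publication at 2 years.

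**Working it through.** **The plan's own figure.** Inputs from section 10.2: 10% in both arms, margin 0.05, one-sided alpha 0.05, power 80%, unpooled z-test.

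n = (1.645 + 0.842)² × (0.09 + 0.09) / 0.05² ≈ 445.1, rounded up to 446 per group. This matches. Power is 80.1% at 446 per arm and 86.3% at 540 per arm (half of 1,080).

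**Adding detection.** Let p be the occult prevalence at entry, equal in both arms by randomization and fully revealed by excision. Let s be the share of it diagnosed in AM by 2 years, and e the true excess of new invasive cancer in AM, all of it diagnosed.

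- Observed surgery rate = p
- Observed AM rate = p·s + e
- Observed difference = e − p(1 − s)

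The rule compares the observed difference with 5 points, so in effect it compares e with 5 + p(1 − s) points.

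The probability of declaring non-inferiority is Φ((0.05 − observed difference)/SE − 1.645), with SE the unpooled standard error of the observed difference. The table takes a true excess exactly at the margin (e = 5 points) and 446 per arm. Each cell shows the effective margin in points, then that probability.

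| p | s = 1 | s = 0.75 | s = 0.5 |
|---|---|---|---|
| 0% | 5; 0.05 | 5; 0.05 | 5; 0.05 |
| 5% | 5; 0.05 | 6.25; 0.18 | 7.5; 0.46 |
| 10% | 5; 0.05 | 7.5; 0.32 | 10; 0.80 |
| 20% | 5; 0.05 | 10; 0.59 | 15; 0.99 |

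Worked cell, p = 10%, s = 0.5: AM observed = 5% + 5% = 10%; difference 0; SE = √(0.18/446) = 0.0201; 0.05/0.0201 − 1.645 = 0.844; Φ = 0.80. About 22 of 446 AM women (446 × 0.10 × 0.5) would carry an undiagnosed cancer counted as a non-event.

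With 540 per arm, p = 10% and s = 0.5, the probability is 0.86 at e = 5 points and 0.47 at e = 7 points. With full detection the two figures are 0.05 and 0.005.

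**Room in the rule.** With surgery observed at 10% and 446 per arm, AM passes at any observed rate up to about 11.6%. If both arms were observed at 10%, adding back about 1.6 points of undetected cancer would reach that limit. With p = 10% this is s = 1 − 1.6/10 = 0.84.

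**Cover elsewhere in the plan.** The sensitivity analyses in 10.2 (per protocol, as treated, instrumental variable, principal stratification) address rejected allocation, withdrawal and loss to follow-up. None varies detection by arm. In the event definitions of 10.2, ipsilateral nodal disease counts only if no ipsilateral invasive cancer came before it, so node-positive and node-negative invasive cancers score alike.

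**The case against.** There is a serious case on the other side, and much of it stands.

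- **AM is monitored.** A reader might infer that AM leaves occult invasion unseen. The documents do not support that. AM has 6-monthly examination and mammography with biopsy criteria, and its imaging of the affected breast is twice as frequent as in the surgery arm (6.1.1, 6.1.2). Some occult cancers will be diagnosed by 2 years; the share is not given.
- **Later endpoints exist.** A reader might infer that nothing in the plan measures delayed diagnosis. That is also too strong. A cancer missed at 2 years and found later counts in the 5-, 7- or 10-year invasive rate. Cancer-specific survival and chemotherapy rate are indirect signals. Nodal disease, distant metastasis or breast cancer death can count as the event under the first-occurrence rules in 10.2. What remains is that these are late or indirect, and none gives size, nodes or stage at diagnosis.
- **The estimand is already diagnosis.** Sections 2.1, 10.1 and 10.2 speak of diagnosis or detection, and the 5% margin is set for that quantity. The plan sets no margin for cancer actually present, so exceeding 5 points on that scale breaks no rule of the plan. The gap is with the broader claim in 1.4.
- **The numbers rest on assumptions.** At p = 0 there is no bias. Entry criteria shrink the pool: masses are largely excluded, a second biopsy site is required above 4 cm, and two pathologists must agree. The model also assumes full acceptance of allocation and, with e read as an excess, full detection of new cancers. That last assumption is not the one that inflates the effect. If AM diagnosed 75% of all its cancers at a true rate of 15%, the probability of passing would be 0.57, against 0.32 when only 75% of the occult ones are found.

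**Conclusion.** The point holds in a limited form. The 2-year comparison is valid for diagnosed ipsilateral invasive cancer, and its sample size reproduces. Ascertainment of occult invasion differs by arm in a direction that favours non-inferiority, and no planned analysis examines this. No endpoint directly records the size, nodal status or stage that would show the consequence of the delay named in 1.6.

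The size cannot be fixed from the documents. On the plan's own 10%, the effective margin on cancer present is 7.5 points if AM finds three quarters of the occult cases by 2 years and 10 points if it finds half. Across p = 0-20% and s = 0.5-1 it runs from 5 to 15 points. These figures are illustrations under assumed p and s, not estimates of bias in this trial.

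A reader might go on to infer that the primary test is invalid or that AM will pass wrongly. The documents support neither. The change is worth making because the bias is of unknown size, runs in the favourable direction, and can be bounded at low cost.

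**What to change.** Leave the primary test, margin and sample size as they are, and make four changes.

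1. **Section 2.3.2:** add a secondary intention-to-treat endpoint over all randomised women: cumulative incidence by arm, at 2, 5, 7 and 10 years, of ipsilateral invasive cancer that is node-positive or above a prespecified size (for example, larger than 2 cm) at diagnosis. The cut is the trial team's to fix in advance. The data can be abstracted from reports that section 6.1.1 already collects: all radiology "and pathology reports as well as the primary source image data will be uploaded".
2. **Section 10.2, reporting:** split invasive events in each arm into those found at an operation without prior biopsy-proven invasion and those diagnosed by biopsy. Keep AM women who elect surgery in follow-up for this purpose. Section 5.2.2.1 offers them continued follow-up, while 10.7 can be read as recording them as withdrawn and censoring them; reconcile the two. Their upstaging rate gives a rough view of what AM has not yet found, but the group is self-selected, and the report should say so.
3. **Section 10.2, sensitivity:** add a tipping-point analysis of the 2-year difference over p and s, adding p(1 − s) to the observed difference. The surgery arm's own upstaging rate can anchor p. This step is essential, because the endpoint in item 1 is itself based on diagnosis and cannot see cancers not yet found.
4. **Conclusion:** word the 2-year result as non-inferiority of diagnosed invasive cancer, to be read with items 1-3 and the 5-year invasive rate.

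The cost is an amendment to the endpoint and analysis text, plus abstraction of size and nodes. Advanced-stage events will be few, intervals wide, and the 2-year claim more guarded.
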